## Methodology:

This is a 2-part, randomized, placebo-controlled, double-blind, Phase 2 study to evaluate the safety, tolerability, efficacy, of RTA 901 in qualified subjects with DPNP. While on the study, subjects will take only 1 prescribed standard-of-care (SOC) pain medication (duloxetine, pregabalin, or gabapentin) at a stable dose (Section 7.8.1) and a single rescue medication, as needed, to treat DPNP (Section 7.8.3).

The duration of each part of the study will be approximately 20 weeks, including a Screening Period of up to 2 weeks, a Run-in Period of 2 weeks, a Treatment Period of 12 weeks, and a Follow-up Period of 4 weeks. All subjects in Part 1 and Part 2 of the study will follow the same visit and assessment schedule. Procedures will be performed according to the Schedule of Assessments.

[figure not shown]
Screening Period (Days -28 to -15): Includes 1 clinic visit up to 2 weeks prior to the Run-in Period (within 28 [± 2] days prior to Day 1). Daily NPRS and DSIS will be collected using an e-diary from Screening to the end-of-study visit. Washout from prohibited medications is allowed if the Investigator deems it medically appropriate; the washout period must cover 5 half-lives of the prohibited medication and must be completed prior to the end of the Screening Period, or in the case of NSAIDs for DPNP, washout must be completed prior to the last 7 days of Screening.

Run-in Period (Days -14 to -1): Includes 1 clinic visit which must occur during a  $14 (\pm 2)$ -day period prior to Day 1. Subjects who continue to successfully meet the Run-in eligibility criteria will receive single-blind placebo once daily in the morning in addition to their SOC pain medication. All study drug should be administered in an early fasted state, defined as having no food within at least 2 hours prior to study drug administration and for 1 hour following study drug administration. Daily NPRS scores will continue to be collected using the e-diary. Pain intensity and rescue medication use will also continue to be recorded daily at bedtime in the e-diary. Subjects will also complete the DSIS upon waking.

- Subjects in Part 1 who remain eligible after the Run-in period will be randomized 1:1:1 to either RTA 901 (10 or 80 mg) or placebo at Day 1 (randomization),
- Subjects in Part 2 who remain eligible after the Run-in period will be randomized 1:1:1 to either RTA 901 (Dose 1 or Dose 2) or placebo at Day 1 (randomization).

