## 2.1.2. Secondary Objectives

- To assess the efficacy of RTA 901 in achieving at least 30% decrease in the NPRS pain intensity score after 12 weeks of treatment
- To assess the efficacy of RTA 901 in achieving at least 50% decrease in the NPRS pain intensity score after 12 weeks of treatment
- To assess the percentage of subjects using rescue medication for DPNP treatment during the Treatment Period, as well as the quantity and timing of such medication use during the Treatment Period
- To assess the Daily Sleep Interference Scale (DSIS) score after 12 weeks of treatment

Version 4.0

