#### 7.8.3. Rescue Medication

Rescue medication for DPNP is in addition to standard of care medication (gabapentin, pregabalin or duloxetine) for DPNP. Rescue medication is intended to treat temporary elevations in a subject's DPNP and is intended to be used occasionally and not meant to be used for prolonged periods of time.

Subjects who enter screening after implementation of protocol Version 4.0 may only use acetaminophen as a rescue medication for DPNP as needed. If rescue medication is needed for DPNP, subjects will be instructed to take acetaminophen 500 mg every 4 to 6 hours as needed (not to exceed 3000 mg per day).

Subjects currently in the study at the time of implementation of protocol Version 4.0 using ibuprofen as rescue medication for DPNP may switch their rescue medication to acetaminophen (i.e., no longer use ibuprofen as a rescue medication for DPNP) or continue to use as rescue medication for DPNP ibuprofen 200 to 400 mg every 4 to 6 hours as needed (not to exceed 600 mg/day) for up to 3 days in a 7-day period (not calendar week). Subjects unable to comply with these conditions will need to discontinue study treatment and withdraw from the study; some or all of such subjects may be replaced at the discretion of the Sponsor.

The daily maximum dosages stated in this section are inclusive of those used outside of treatment for DPNP. Any questions related to rescue medications should be directed to the Medical Monitor prior to administration when possible.

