5.7.3. Rescue Medication

Rescue medication for DPNP is in addition to standard of care medication (gabapentin, pregabalin or duloxetine) for DPNP. Rescue medication is intended to treat temporary elevations in a subject's DPNP and is intended to be used occasionally and not meant to be used for prolonged periods of time.

Prior to implementation of protocol 4.0, if rescue medication is needed, subjects will be instructed to take acetaminophen 500 mg every 4 to 6 hours as needed (not to exceed 3000 mg per day) or ibuprofen 200 to 400 mg every 4 to 6 hours as needed (not to exceed 1200 mg per day) (protocol version 3.0).

Subjects who enter screening after implementation of protocol Version 4.0 may only use acetaminophen as a rescue medication for DPNP as needed. If rescue medication is needed for DPNP, subjects will be instructed to take acetaminophen 500 mg every 4 to 6 hours as needed (not to exceed 3000 mg per day).

Subjects currently in the study at the time of implementation of protocol Version 4.0 using ibuprofen as rescue medication for DPNP may switch their rescue medication to acetaminophen (i.e., no longer use ibuprofen as a rescue medication for DPNP) or continue to use as rescue medication for DPNP ibuprofen 200 to 400 mg every 4 to 6 hours as needed (not to exceed 600 mg/day) for up to 3 days in a 7-day period (not calendar week). Subjects unable to comply with these conditions will need to discontinue study treatment and withdraw from the study; some or all of such subjects may be replaced at the discretion of the Sponsor. The daily maximum dosages stated in this section are inclusive of those used outside of treatment for DPNP. Any questions related to rescue medications should be directed to the Medical Monitor prior to administration when possible.

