6.1. General considerations for efficacy endpoints

All efficacy analyses will be performed on the scheduled visits/study weeks for the ITT population. For NPRS and DSIS, the visit refers to study week.

The primary hypothesis is to test if there is a greater mean reduction from baseline in NPRS pain intensity for the RTA 901-treated groups compared with placebo after 12 weeks of double-blind treatment.

Stratification factor (standard of care) will not be included for any modelling due to <10 patients of randomized patients taking duloxetine at randomization.

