6.4.4. Quantity and timing of rescue medication use

The amount of rescue medication used per day during the 12-week treatment period will be calculated as the total dosage recorded divided by total days of study drug exposure during the treatment period. The rescue medication used per day will be summarized using the mean, standard deviation, minimum, median and maximum by treatment group. Rank ANCOVA will be performed by category of rescues medication use (Acetaminophen, NSAIDs). The model will include rank of baseline NPRS and treatment group. P-value for the comparisons of RTA 901 group (10mg, 80mg) vs placebo will be presented.

Time to first occurrence of rescue medication use will be calculated for each patient during double-blinded treatment period. If subject had an event, the day of the event will be date of the first date of rescue medication use recorded in e-diary during the treatment period. If a subject withdraws from the study prior to Week 12 and the subject did not take any rescue medication, then the subject will be censored on the last day they were in the study. The start date for time to first occurrent of rescue medication use is defined as the date of the first randomized dose. The proportion of first occurrence of rescue medication use will be estimated using the Kaplan-Meier (KM) product limit method and be presented as KM curves over time. The KM estimates of median time to first occurrence of rescue medication use, percentiles (5th,10th,25th, 50th and 75th) and associated 95% confidence limits will be presented. P-value from log-rank test will be presented.

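### SAP 6.4.4 tests rescue quantity only within each product and leaves non-users of a product undefined, so the secondary objective of overall rescue quantity has no test

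*SAP*

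**What the plan says.** Protocol 2.1.2 sets a secondary objective on the percentage of subjects using rescue for DPNP, "as well as the quantity and timing of such medication use during the Treatment Period". It does not divide this by product.

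SAP 6.4.4 derives rescue per day as the recorded total dosage "divided by total days of study drug exposure during the treatment period". A descriptive summary by treatment group follows. The inferential step is "Rank ANCOVA will be performed by category of rescues medication use (Acetaminophen, NSAIDs", with this specification: "The model will include rank of baseline NPRS and treatment group". There is no term for product or protocol version, and no rank ANCOVA for rescue as a whole.

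Several passages determine which product a subject takes:
- The protocol synopsis (Methodology) has each subject on "a single rescue medication, as needed, to treat DPNP".
- SAP 5.7.3 records that acetaminophen or ibuprofen could be used before Version 4.0.
- Under Protocol 7.8.3, subjects entering screening after Version 4.0 took effect "may only use acetaminophen as a rescue medication for DPNP as needed".
- Under SAP 5.7.3, ibuprofen users already on study "may switch their rescue medication to acetaminophen", or may continue ibuprofen within a daily dose cap and a limit of 3 days in 7.

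On population, SAP 6.1 gives a general rule: "All efficacy analyses will be performed on the scheduled visits/study weeks for the ITT population". SAP 6.4.4 does not repeat it or say how a non-user of a product is scored. SAP 6.2 plans no formal testing of secondary endpoints.

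**The concern.** A drug that spares rescue should lower total use. Dividing that total by product spreads the effect over two tests, and neither of them measures the stated objective. The section allows two readings.

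- **Zeros kept.** An ibuprofen user is a zero in the acetaminophen test whatever the drug does. A Version 4.0 entrant is a zero in the NSAID test by rule. A subject who switched has each product's dose spread over all exposure days and looks like a light user of both.
- **Users only.** Each test compares only those who took the product after randomization, and drops subjects whom the drug spared from rescue altogether.

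The first reading costs power. The second gives up the randomized comparison. Part 1 exists to inform dose selection (SAP 2.4), so a weak or ambiguous rescue result would carry less information into that decision.

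**Working it through.** **1. The plan's own power figure.** SAP 2.4 gives about 80% power with 64 per arm, difference 1.2, SD 2.4 and two-sided 0.05. The standardized shift is 1.2 / (2.4 × √(2/64)) = 2.83, and Φ(2.83 − 1.96) gives 80.7% (80.2% by the noncentral t). The figure reproduces, but it applies to NPRS. The documents give no power, rescue rate or product share for rescue quantity.

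**2. Simulation set-up.** From the SAP: 64 versus 64, two-sided 0.05, and rank(quantity) regressed on rank(baseline) and arm. The following are assumptions, not document figures:
- Placebo rescue use is 90%, 70% or 50%, with 15%, 25% or 40% fewer users respectively on active drug.
- The amount among users is lognormal (log SD 1), lower by 0.45, 0.45 or 0.40 log units on active drug. It correlates 0.3 with baseline.
- Product is independent of arm, and nobody switches.
- The acetaminophen share is 50%, 70% or 90%.

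Each setting has 4000 runs, so the simulation standard error is at most √(0.25/4000) = 0.8 percentage points. The combined test uses the amount on a common, product-neutral scale.

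**3. Results with zeros kept.** Loss = 1 − split power / combined power. For example, 1 − 23.4/87.5 = 73%.

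| Acetaminophen share | Placebo use | Combined power | Acetaminophen power (loss) | NSAID power (loss) |
|---|---|---|---|---|
| 50% | 90% | 87.5% | 23.4% (73%) | 22.0% (75%) |
| 50% | 70% | 77.5% | 26.0% (66%) | 26.4% (66%) |
| 50% | 50% | 73.3% | 31.7% (57%) | 32.0% (56%) |
| 70% | 90% | 87.0% | 44.0% (49%) | 10.0% (89%) |
| 70% | 70% | 77.4% | 43.8% (43%) | 14.1% (82%) |
| 70% | 50% | 74.2% | 49.8% (33%) | 19.7% (73%) |
| 90% | 90% | 87.0% | 74.8% (14%) | 6.0% (93%) |
| 90% | 70% | 77.6% | 66.9% (14%) | 7.1% (91%) |
| 90% | 50% | 74.5% | 66.8% (10%) | 8.9% (88%) |

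**4. Users only.** At a 90% share the acetaminophen test has 60.6%, 46.9% and 24.8% power. The losses are 1 − 60.6/87.0 = 30%, 1 − 46.9/77.6 = 40% and 1 − 24.8/74.5 = 67%.

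**5. Error rate.** With no drug effect, 70% use and an even share, the combined test rejects in 4.6% of runs and the zeros-kept split tests in 5.2% and 5.0%. At least one of those two rejects in 9.0%.

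**6. Rescue days instead of amounts.** A second simulation (2000 runs per setting) drew daily use from a logit-normal probability with mean logit −2, −3 or −4 and SD 2, and lowered the log-odds by 1 on active drug. One test of product-free rescue days had 66-78% power. The acetaminophen-only test had 17-24%, 34-36% and 55-62% at shares of 50%, 70% and 90%. The pattern is the same under different assumptions.

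**The case against.** The case for leaving the section alone has several parts.

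- **The split has a reason.** Milligrams of acetaminophen and ibuprofen are not additive. This stands, and it is why the by-product milligram results should stay.
- **Other rescue analyses combine products.** Any use, with a logistic model at Week 12 (SAP 6.4.3), and time to first use (SAP 6.4.4) are not split. This stands for percentage and timing. Neither measures quantity: a subject with one rescue day and a subject with eighty can count alike.
- **The p-values are non-formal.** This stands (SAP 6.2) and limits the consequences. They are still to be presented.
- **The users-only reading is unlikely.** A reader might infer from the by-category wording that the SAP conditions on use. SAP 6.1 and the ITT definition in SAP 3.6 point the other way. What remains is that 6.4.4 does not say so.
- **Not every zero is imposed by rule.** Acetaminophen was open to subjects under both versions, so only the NSAID test has zeros forced by protocol version. The zeros-kept tests also hold their error rate. The fault is therefore lost efficiency and an untested objective, not bias.
- **Rescue days are imperfect.** They ignore tablets per day, and the Version 4.0 day limit touches continuing ibuprofen users. This stands as a reason to add the measure beside the milligram analysis and not in place of it. The limit applies equally in all arms.

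**Conclusion.** The point holds as a gap in the quantity analysis. No planned test addresses overall rescue quantity, and the handling of non-users of a product is unstated.

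With zeros kept, the cost depends on the product share. At an even share each test loses 56-75% of the combined power. At 70:30 the acetaminophen test loses 33-49% and the NSAID test 73-89%. At 90:10 the acetaminophen test loses 10-14%, and the NSAID test has 6-9% power. These sizes rest on assumed rescue rates, effects and shares, and on no switching.

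A reader might infer that each split test always loses most of its power. The documents do not support that. They give no share, and acetaminophen could well dominate because Version 4.0 allows new entrants nothing else. The main test would then keep most of its power. Nor does any formal conclusion of Part 1 turn on these p-values. This is an inexpensive improvement, not a threat to the trial's primary result.

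**What to change.** In SAP 6.4.4:
1. State that every ITT subject enters each quantity analysis, with zero for a product not taken.
2. Add one product-neutral rank ANCOVA for each dose versus placebo. The outcome is the percentage of diary days in Study Days 1-84 with any DPNP rescue (acetaminophen or ibuprofen), zeros kept, with ranked baseline NPRS and treatment as now. Study Days 1-84 match the Week 1-12 NPRS windows in SAP Table 2. Say how a subject with no rescue diary entries is handled.
3. Keep milligrams per day by product as supportive results.
4. Repeat that these p-values are non-formal, in line with SAP 6.2.

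The cost is a few sentences and one derived variable, since rescue use is already recorded daily in the e-diary. The new measure does not see the number of tablets taken in a day, which the milligram results still show. It is also affected by the Version 4.0 day limit for continuing ibuprofen users, equally in all arms.

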6.4.5. Change from baseline in the DSIS

The DSIS is a numeric scale, ranging from 0 representing no interference with sleep to 10 representing complete inability to sleep. The subject selects a whole number (0 to 10) that best indicates his/her ability to sleep in the past 24 hours. The DSIS will be completed daily by subjects upon waking (3-minute self-administered questionnaire).

The weekly mean is defined as the sum of non-missing daily scores divided by the number of days with non-missing scores for that week. Subjects with fewer than 3 daily scores during an analysis week will be considered to have a missing weekly average for that week.

[figure not shown]
No imputation will be conducted at weekly average level.

Descriptive statistics for observed data, including actual value and change from baseline in weekly average DSIS score, will be evaluated by treatment group and visit (including EOS visit) with descriptive statistics (mean, SD, median, 1st and 3rd quartiles, range) in the ITT population.

Change from baseline in weekly DSIS average score will be analyzed through MMRM model. The MMRM model will include baseline DSIS score, visit, treatment, the interaction of treatment and visit, the interaction of baseline DSIS score and visit. Unstructured covariance will be used. All analysis visits up to Week 12 will be utilized. In the event that convergence issue occurs, similar subsequent steps will follow described in section 6.3

LS means and treatment differences will be presented with 95% confidence intervals, standard errors, p-values at each visit. A line plot of LS mean changes from baseline over time will also be provided.

A sensitivity analysis will be performed excluding any data after a subject discontinued randomized study treatment.

Product: RTA 901 (BIIB143)

Study: 901-C-2102 Version: 1.0

Statistical Analysis Plan

Product: RTA 901 (BIIB143)

Study: 901-C-2102 Version: 1.0

Statistical Analysis Plan

Product: RTA 901 (BIIB143) Statistical Analysis Plan Study: 901-C-2102 Version: 1.0

7. Safety endpoints

All analyses of the safety data are performed using the safety analysis set. Descriptive statistics are presented by treatment group actually received in the safety analysis set. No statistical testing will be performed on the safety data.

7.1. Adverse Events

All AEs will be classified using MedDRA. In this study, only treatment emergent AEs (TEAEs) i.e. those that occurred or worsened after the first randomized dose will be analyzed. Such AEs will have an onset date on or after the date of first randomized dose or will have presented prior to the first randomized dose and subsequently worsened. Therefore, whenever an analysis of summary of AEs is mentioned, it is intended that this is in reference to treatment-emergent AEs.

Whenever possible, date/time will be used to determine whether an event is treatment emergent. If an event date (start or end) is incomplete, a TEAE will be determined assuming the most conservate way as follows:

- If onset day is missing and the month and year are the same as or after the treatment start date, then that event is considered treatment emergent.
- If both onset month and day are missing and the year is the same as or after the treatment start date, then that event is considered treatment emergent.
- If both onset date and end date are completely missing, an event will be considered as a TEAE.
- If onset date is completely missing and end date is not missing which is after the first randomized dose of study drug, an event will be considered as a TEAE.

The incidence of TEAEs will be summarized by dose level (or cohort) and overall RTA 901 as follows:

- Overall summary of TEAE
- TEAEs by primary SOC and MedDRA preferred term
- TEAEs by MedDRA preferred term
- TEAEs by MedDRA preferred term with incidence of >=2%
- SAEs by primary SOC and MedDRA preferred term
- SAEs by MedDRA preferred term
- Related SAEs by primary SOC and MedDRA preferred term
- TEAEs by maximum severity, primary SOC and MedDRA preferred term
- Related TEAEs by primary SOC and MedDRA preferred term
- TEAEs that led to discontinuation of study treatment by primary SOC and MedDRA preferred term
- TEAEs that led to study drug interruption by primary SOC and MedDRA preferred term
- TEAEs that led to withdrawal from study by primary SOC and MedDRA preferred term

TEAEs that led to death by primary SOC and MedDRA preferred term

For the summary of TEAEs by severity, primary system organ class and/or preferred term, participants will be counted only once within each primary SOC/MedDRA preferred term and will only be counted under the maximum severity.

For the summary of TEAEs by relationship to study treatment, a subject will be counted only once and in the category of the strongest relationship to study treatment within each SOC/preferred term. The relationship to study treatment will be classified as related or not related.

Also, the AEs during the run-in period will be summarized by primary SOC and MedDRA preferred term.

Listings of all AEs, SAEs, AEs that led to study drug discontinuations, AEs that led to study withdrawals, and AEs that led to study drug interruption will be presented. Listing of death will be provided.

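### SAP 7.1 classifies adverse events with a partial onset date without checking the end date, so an event that ended before the first randomized dose can be counted as treatment-emergent

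*SAP*

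**What the plan says.** SAP 7.1 restricts the adverse event analysis to treatment-emergent events, meaning "those that occurred or worsened after the first randomized dose will be analyzed". It then introduces the handling of dates in two sentences. The first is general: "Whenever possible, date/time will be used to determine whether an event is treatment emergent". The second sends incomplete dates to a list: "If an event date (start or end) is incomplete, a TEAE will be determined assuming the most conservate way as follows".

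Four bullets follow.

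- **Bullet 1, onset day missing.** The event is treatment-emergent under this condition: "If onset day is missing and the month and year are the same as or after the treatment start date". There is no end-date condition.
- **Bullet 2, onset month and day missing.** The condition is "If both onset month and day are missing and the year is the same as or after the treatment start date". Again there is no end-date condition.
- **Bullet 3, onset and end both wholly missing.** The event is treatment-emergent.
- **Bullet 4, onset wholly missing but end date known.** The condition is "If onset date is completely missing and end date is not missing which is after the first randomized dose of study drug". This is the only bullet that compares an end date with the start of randomized treatment.

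SAP 7.1 also plans a separate summary of adverse events in the Run-in period.

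**The concern.** The definition and the bullets can give opposite answers for the same event. If an event is known to have ended before the first randomized dose, it cannot have begun or worsened after that dose, so by definition it is not treatment-emergent. Bullets 1 and 2 nevertheless count it whenever its onset month (or year) matches the month (or year) of treatment start.

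The list is also internally inconsistent. With the onset wholly missing, bullet 4 lets a known pre-dose end date keep the event out. With the onset partly known, the same end date is ignored. More onset information leads to the wrong answer and less leads to the right one.

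Such events can be in the database. Protocol 5.1.6 starts adverse event reporting at consent, Protocol 3.1 allows up to 2 weeks of Screening and 2 weeks of Run-in before Day 1, and Protocol 6.3.3 requires the resolution date to be collected. At stake is the accuracy of the TEAE flag. That flag decides which events enter the TEAE tables, and these report the safety endpoint that the protocol lists as primary.

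**Working it through.** The plan states no figure on this point, so there is none to reproduce. The check has two parts: applying the rules to test cases, and asking how much of the pre-dose period they can reach.

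**1. The rules applied as written.** Take a first randomized dose on 25 March 2024. The last column adds one condition: a known end date before the first randomized dose means not treatment-emergent.

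| Onset recorded | End date | Deciding rule | As written | With end-date condition |
|---|---|---|---|---|
| March 2024, day missing | 15 Mar 2024 | bullet 1 | TEAE | not TEAE |
| 2024, month and day missing | 15 Mar 2024 | bullet 2 | TEAE | not TEAE |
| wholly missing | 15 Mar 2024 | bullet 4 not met | not TEAE | not TEAE |
| 10 Mar 2024 | 15 Mar 2024 | complete dates | not TEAE | not TEAE |
| February 2024, day missing | 15 Mar 2024 | bullet 1 not met | not TEAE | not TEAE |
| March 2024, day missing | missing | bullet 1 | TEAE | TEAE |
| March 2024, day missing | 2 Apr 2024 | bullet 1 | TEAE | TEAE |

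Only the first two rows change. Rows 3 and 4 are the same event with less and with more onset information, and both are classified correctly. The last two rows show that the added condition leaves the conservative treatment of truly uncertain events as it is.

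**2. Share of pre-dose days that the rules can reach.** Inputs: 14 Run-in days, and 28 pre-dose days in all (a maximum, because Screening is up to 2 weeks). Assumption: Day 1 is equally likely to be any day of a calendar year, here the 366 days of 2024.

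*Same month (bullet 1).* If Day 1 is day d of its month, the number of the n pre-dose days in that month is min(d − 1, n). Summing over d:

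- n = 28: 462 for a 31-day month, 434 for a 30-day month, 406 for a 29-day month. Over the year, 7 × 462 + 4 × 434 + 406 = 5,376. Divided by 28 × 366 = 10,248, this is 52%.
- n = 14: 329, 315 and 301. Over the year, 7 × 329 + 4 × 315 + 301 = 3,864. Divided by 14 × 366 = 5,124, this is 75%.

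*Same year (bullet 2).* Pre-dose days falling in the previous year sum to n + (n − 1) + … + 1.

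- n = 28: 1 − 406/10,248 = 96%.
- n = 14: 1 − 105/5,124 = 98%.

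These are shares of days on which an event could meet the rule. They are not expected counts of misclassified events. A misclassification also needs a partial onset date and an end date that is known and falls before the first randomized dose, and the documents give no rate for either.

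**The case against.** The strongest reply is that the bullets should be read with the sentence that precedes them: "Whenever possible, date/time will be used to determine whether an event is treatment emergent". If a complete end date falls before the first dose, the dates already settle the matter and no fallback is needed. Bullet 4 supports this as the likely intent. What stands is that the intent may well be right. But the next sentence sends any event with an incomplete start or end date to the bullets, and these contain no override. A programmer who follows them will flag the event.

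A second reply is that over-inclusion is a declared, conservative choice that never hides an event. That is a sound way to resolve uncertainty, but a known pre-dose end date leaves none to resolve.

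Other defences limit the size, and they stand. Safety data are not formally tested (SAP 7), all adverse events are listed, and the error has no reason to favor one arm. Adverse events are assessed at Screening, Run-in and Day 1, so recall is short. Missing data are queried with the site (Protocol 9.4.5), so partial dates should be uncommon.

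Three stronger readings are tempting, and the documents do not support them.

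- **A count of wrong events.** A reader might assume, say, 40 pre-dose events with 5% to 10% lacking an onset day. That gives 2 to 4 events, and a same-month share of about one half gives 1 to 2 errors. Both inputs are assumptions, and the result is at best a ceiling because it treats every such event as having a known pre-dose end date.
- **Every safety table is affected.** Protocol 6.1.1 and 6.3.4 make causality not applicable for events before study drug, so Screening events should not reach the related-event tables. Run-in events might, because Protocol 7.1 counts placebo as study drug and Run-in subjects take it.
- **A pre-dose serious event listed as treatment-emergent.** This is possible but remote. Protocol 6.4 requires serious events to be reported within 24 hours of site awareness with supporting documents, and such an event would have to lack an onset day despite that and despite data queries.

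**Conclusion.** The point holds as a defect in a stated rule. As written, bullets 1 and 2 of SAP 7.1 count a partial-onset event as treatment-emergent even when its recorded end date is before the first randomized dose. This contradicts the SAP's definition and is out of step with bullet 4.

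The size is unknown and probably very small. Bullet 1 can reach only events whose onset month is the month of first dose, and bullet 2 only those whose onset year is the year of first dose. The end date must also be recorded and pre-dose. The 52% and 96% shares rest on the uniform Day 1 assumption and a full 28-day pre-dose period, and describe reach only.

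The error can only add events, in any arm, to descriptive TEAE tables. It could place one Run-in event in both the Run-in summary and the TEAE summary, and could affect related-event tables at most through Run-in events. It has no bearing on the efficacy analyses or on power. This is a low-priority correction, worth making because it is simple.

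**What to change.** Add one clause to bullets 1 and 2 of SAP 7.1: *unless the end date, complete or partial, shows the event resolved before the first randomized dose*. A partial end date would meet this only if its month or year is earlier than that of the first randomized dose. Events whose end date is missing or falls after the first dose keep their present classification, so the conservative intent is preserved.

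The cost is one clause in the SAP and one condition in the program that derives the TEAE flag. No new data are needed, because the resolution date is already collected.
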